# 14.2. Secondary Efficacy

The secondary efficacy analyses will be performed for the FAS.

### 14.2.1. Secondary Efficacy Variables & Derivations

- 14.2.1.1. Change from baseline (CFB) to week 24 in the Patient Global Impression of Severity (PGI-S) Patient Global Impression of Severity (PGI-S):
  - Severity of symptoms over the past week (1-week recall)
  - overall experience of symptoms over the past 2 weeks (2-week recall)

are both rated on a 4-point type Likert scale, with scores ranging from 1 (none), 2(mild), 3(moderate) and 4 (severe).

Positive PGIS change (1, 2, 3) indicates worsening, while negative PGIS change (-1, -2, -3) indicates improvement while considering change from baseline to week 24 for both 1 week recall and 2 week recall results separately using the FAS for the IAWK12 and IAWK24.

**Table I:** PGIS Change

Improved 3 categories	CFB = -3
Improved 2 categories	CFB =-2
Improved 1 categories	CFB =-1
No Change	CFB =0
Worsened 1 category	CFB =+1
Worsened 2 categories	CFB =+2
Worsened 3 categories	CFB = +3

The number and percentage of participants with each PGI-S score will be summarized by treatment and time point, for the FAS. Number and percentages will also be presented for CFB categories for both 1 week recall and 2 week recall responses separately using the FAS for the IAWK12 and IAWK24..

These PGI-S score will further define as Improvement (with CFB as -3, -2 or -1), No Change (with CFB as 0) and Worsening (with CFB as +1, +2, +3).

Document: BIOSdata\argenx\Efgartigimod\HAB40220\Biostatistics\Documentation\SAP

Author: Version Number: 3.0

Version Date: 02 May 2024

Template No.: CS\_TP\_BS016 Revision 7 Reference: CS\_WI\_BS005

Page 40 of 64

The proportion of efgartigimod and placebo participants with improvement at week 24 will be compared using, a fisher's exact test, based on observed data for both the 1 week recall and 2 week recall results using the FAS for the IAWK12 and IAWK24.

#### 14.2.1.2. Patient Global Impression of Change (PGI-C) at week 24

The Patient Global Impression of Change (PGI-C) is a single item designed to capture the subject's perception of change in their overall symptom severity. Overall change in symptoms from the start of IMP to time point is rated on a 7-point Likert scale, with scores ranging from Much Better (1), Somewhat Better (2), A Little Better (3), No change (4), A Little Worse (5), Somewhat Worse (6), and Much Worse (7).

The number and percentage of participants with each PGI-C score will be summarized by treatment and time point, for the FAS for IAWK12and IAWK24.

These PGI-C score will further define as Improvement (those reporting "Much better", "Somewhat better", or "A little better"), No Change (those reporting "No change") and Worsening (those reporting "A little worse", "Somewhat worse" or "Much worse").

The proportion of efgartigimod and placebo participants with improvement at week 24 will be compared using a fisher's exact test, based on observed data for IAWK12 and IAWK24 using the FAS.

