This study aims to evaluate the efficacy and safety of weekly infusions of efgartigimod IV 10 mg/kg compared to matched-placebo IV in adult participants with post–COVID-19 POTS.

After an up to 28-day screening period, eligible participants will be randomized to efgartigimod IV 10 mg/kg or placebo in a 2:1 ratio, respectively, at baseline. IMP will be administered weekly during the 24-week randomized treatment period. At the end of the randomized treatment period, eligible participants may roll over into an open-label extension (OLE) study ARGX-113-2105 or remain in this study through the end of the 56-day follow-up period.

Number of Participants:

Approximately 42 participants will be randomized to IMP (efgartigimod IV 10 mg/kg or placebo).

Note: Enrolled means the participant agrees to participate in the clinical study after completing the informed consent process.

Study Arms and Duration:

Each participant will participate in the following study periods:

[figure not shown]
- Screening period of approximately 4 weeks
- Treatment period of 24 weeks
- Follow-up period of approximately 8 weeks (56 days \pm 3 days) for participants who do not roll over to the OLE study ARGX-113-2105

Participants will receive IMP weekly during the 24-week treatment period, with the final weekly dose administered at week 23.

Data Monitoring/Other Committee: No

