6.3. Assignment to Study Intervention

Participants whose eligibility has been confirmed will be randomized using interactive response technology (IRT) in a 2:1 ratio to efgartigimod or placebo, respectively. The preplanned randomization list will be produced using permuted blocks.

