9.1. Statistical Hypothesis

No formal hypothesis will be tested in this phase 2 study. Primary endpoints COMPASS 31 and Malmö POTS will be analyzed using longitudinal mixed model repeated measures using the change from baseline as the response value. Prognostic variables are baseline and visit by treatment interaction using an unstructured variance covariance matrix. The treatment effect and 95% CIs will be estimated at week 24 using an appropriate contrast. Inference will be based on the precision of the estimation rather than hypothesis testing.

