#### 6.6. Statistical Tests

The default significant level will be 5%; confidence intervals (CIs) will be 95% and all tests will be two-sided, unless otherwise specified in the description of the analyses.

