Appendix 1 shows conventions for presentation of data in outputs.

# 7.3. Multiple Comparisons/ Multiplicity

No multiple comparison adjustment or alpha sharing to be considered.

Document: BIOSdata\argenx\Efgartigimod\HAB40220\Biostatistics\Documentation\SAP

Author: Version Number: 3.0

Version Date: 02 May 2024

Template No.: CS\_TP\_BS016 Revision 7 Reference: CS\_WI\_BS005

Effective Date: 01Nov2021

argenx Confidential 29

Page 29 of 64

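### For PGI-S and PGI-C the only planned between-arm result is a Fisher p-value on improved versus not improved, with no effect estimate or confidence interval

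*SAP*

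**What the plan says.** Protocol section 3 lists change from baseline to week 24 in PGI-S and PGI-C at week 24 as secondary endpoints. PGI-S is a 4-point item, so its change runs from -3 to +3. PGI-C is a 7-point item.

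SAP section 14.2.1 tabulates every score by treatment and time point, and for PGI-S every change category. It then groups the categories. For PGI-S, "Positive PGIS change (1, 2, 3) indicates worsening, while negative PGIS change (-1, -2, -3) indicates improvement"; for PGI-C, scores 1 to 3 count as improved. The arms are compared on that dichotomy, using observed data. For PGI-C: "The proportion of efgartigimod and placebo participants with improvement at week 24 will be compared using a fisher's exact test". PGI-S has the same test, run separately for the 1-week and 2-week recall versions. No between-arm estimate or interval is named for either endpoint.

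On inference, protocol section 9.1 states "No formal hypothesis will be tested in this phase 2 study" and, after describing the primary model, "Inference will be based on the precision of the estimation rather than hypothesis testing". SAP section 6.6 sets the defaults: "The default significant level will be 5%; confidence intervals (CIs) will be 95% and all tests will be two-sided". SAP section 7.3 adds "No multiple comparison adjustment or alpha sharing to be considered".

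Elsewhere in the SAP:

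- The primary mixed model (section 14.1.1.1) reports a difference in LS means with SE and 95% CI, plus a p-value.
- PROMIS Fatigue and PROMIS Cognitive (sections 14.2.1.3 and 14.2.1.4) refer back to that model.
- The adverse event overview (section 18.1) includes a 95% CI for the difference in rates, by Agresti-Min or Newcombe depending on group size.

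**The concern.** A study that tests no formal hypothesis has to be read through its estimates and their precision. For the two patient-global endpoints the planned between-arm output is a p-value alone. With about 14 placebo participants, a non-significant Fisher result is likely across a wide range of true effects, and a bare p-value does not let a reader tell a null effect from an imprecise but sizeable one.

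SAP section 3.4 says the information obtained is meant to inform Phase 3 development. That use needs a size of effect and an interval. Choosing the contrast and interval after the results are known would also lose the benefit of pre-specification.

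A secondary issue is that the single comparison counts much better and a little better alike. For PGI-S it also ignores the baseline level, which limits how many categories a participant can improve.

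**Working it through.** **Inputs from the documents.** Protocol section 1.1: "Approximately 42 participants will be randomized to IMP (efgartigimod IV 10 mg/kg or placebo"). Protocol section 6.3: "in a 2:1 ratio to efgartigimod or placebo, respectively". This gives 42 × 2/3 = 28 efgartigimod and 42 × 1/3 = 14 placebo. Tests are two-sided at 5% (SAP section 6.6). The documents give no PGI response rate, effect size, power or precision, so there is no plan figure to reproduce. All rates below are assumptions.

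**1. What a bare p-value leaves out.** Suppose 18/28 versus 6/14 are improved.

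- Proportions: 0.643 and 0.429. Difference d = 0.214.
- Odds ratio: (18 × 8)/(10 × 6) = 2.4.
- Fisher's exact test, two-sided: p = 0.21.
- Wilson 95% limits: 0.458 to 0.793 for 18/28, and 0.214 to 0.674 for 6/14.
- Newcombe lower limit: 0.214 - √[(0.643 - 0.458)² + (0.674 - 0.429)²] = 0.214 - 0.307 = -0.09.
- Newcombe upper limit: 0.214 + √[(0.793 - 0.643)² + (0.429 - 0.214)²] = 0.214 + 0.262 = 0.48.

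The plan would report p = 0.21. The same data say +21 points, 95% CI -9 to +48. Newcombe is used here because it has a closed form. With fewer than 30 per group, the SAP's own rule for adverse events would select Agresti-Min, whose limits need not be identical.

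**2. Actual size of Fisher's test.** Size = sum over all tables with p ≤ 0.05 of the product of two binomial probabilities with equal response rate. At 35% improved it is 3.7% for 28/14 and 2.8% for an assumed 24/12 with data at week 24, against a nominal 5%.

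**3. Power of the dichotomy against an ordinal rank test, PGI-C.** Assumed placebo probabilities for scores 1 to 7: 0.06, 0.10, 0.19, 0.35, 0.15, 0.10, 0.05, so 35% are improved. Fisher's test uses scores 1-3 versus 4-7. The comparator is a tie-corrected Wilcoxon test on all seven scores (simulated).

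*Shift of the whole scale, common odds ratio 4.* The odds of improvement go from 0.35/0.65 = 0.538 to 2.154, so the active rate is 2.154/3.154 = 68%.

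*Movement across the cut only.* Thirty points of active-arm probability move from no change to a little better, so the active rate is 35% + 30% = 65%.

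| Effect, 28/14 | Fisher | Wilcoxon |
|---|---|---|
| Common odds ratio 4 | 49% | 63% |
| No change to a little better only | 41% | 15% |

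The ranking reverses with the shape of the effect.

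**4. PGI-S.** Change was grouped as -2 or less, -1, 0, and +1, with 30% or 40% improved on placebo and 28/14. Under a common odds ratio of 3, Fisher has 32-33% and Wilcoxon 40-42%. Under an odds ratio of 5 the figures are 59-62% and 71-73%. The loss is about 7 to 14 points, again only under a shift of the whole scale.

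**5. Can proportional odds be checked?** With 14 placebo participants over seven PGI-C categories and the probabilities above, about 88% of simulated trials leave at least one placebo category empty.

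**The case against.** Four points can be made for the plan.

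*The data are not lost.* A reader might infer that the plan gives nothing to estimate from. That is not so: every PGI-S and PGI-C category is tabulated by arm, much better stays visible separately from a little better, and a difference can be computed from the counts. What is missing is a pre-specified contrast with its precision.

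*The dichotomy does not always cost power.* A reader might infer that Fisher's test on two classes simply wastes power. The documents give no expected effect shape, and in one plausible shape the dichotomy is clearly better (41% against 15%). The power argument is conditional. It is also secondary in a study that allocates no alpha to these endpoints and is sized on COMPASS 31.

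*There is no PGI-specific protocol method to breach.* In protocol section 9.1 the sentence on precision of estimation closes the description of the COMPASS 31 and MaPS model, and the SAP repeats it for that model only, which itself also reports a p-value. Reading it as a rule that the PGI analysis violates goes too far. The sentence excluding formal hypothesis testing, however, covers the whole study, and a p-value as the sole between-arm result fits poorly with it.

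*A proportional-odds model as the main analysis is debatable.* With 14 placebo participants the assumption can hardly be checked. That stands, and is why the ordinal analysis is proposed as support only.

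None of these supplies the missing estimate and interval.

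**Conclusion.** The point holds as a gap in pre-specification. PGI-S and PGI-C are the only named primary or secondary efficacy endpoints whose planned between-arm result is a p-value without an estimate or CI. The SAP already plans an interval for a difference in proportions for adverse events, so the omission is an inconsistency within the plan. This conclusion rests on the text alone and needs no assumption about response rates.

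The size is best seen in the example: p = 0.21 against +21 points with an interval from -9 to +48. The power figures and Fisher's size (3.7% at 28/14, 2.8% at 24/12) rest on assumed distributions. They support adding an ordinal analysis, not replacing the responder comparison. These are secondary endpoints and no decision rule in the documents depends on the Fisher p-value, so this is a worthwhile and cheap correction that leaves the primary analysis untouched.

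**What to change.** In SAP sections 14.2.1.1 and 14.2.1.2, before week 24 results are seen by treatment:

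1. Make the difference in proportion improved at week 24 (efgartigimod minus placebo), with a 95% CI by the Agresti-Min or Newcombe rule of section 18.1, the main between-arm result for PGI-C and for each PGI-S recall version.
2. Keep Fisher's exact test, with its p-value labelled nominal.
3. Add a supportive analysis using all categories: a common odds ratio or a Mann-Whitney probability with 95% CI. For PGI-S, adjust it for baseline PGI-S.
4. Keep the category tables as they are.

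The cost is a few lines of text and one or two extra outputs per endpoint. No new data are needed. The limitation to state in the SAP is that, with about 14 placebo participants, proportional odds can hardly be assessed, so the common odds ratio should be read as a summary of the overall shift.

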# 14.2.1.3. Change from baseline to week 24 in the Patient-Reported Outcomes Measurement Information System (PROMIS) Fatigue Short Form 8a

PROMIS Fatigue Short Form 8a assesses the impact and perceived fatigue during the last 7 days, through 8-question scale with scores ranging from 1 to 5. Scores are converted to a T-score and received within the eCOA transfers.

The number and percentage of participants with each PROMIS score will be summarized by treatment and time point, for the FAS. T-scores will be descriptively summarized to present absolute value and changes from baseline for each visit for IAWK12 and IAWK24 using the FAS.

For change from baseline to week 24 in PROMIS Fatigue Short Form 8a, between treatment group difference will be analysed using longitudinal mixed model repeated measures (MMRM) as presented in section 14.1.1.1, using FAS except with change from baseline in PROMIS Fatigue as the dependent variable and baseline value

Document: BIOSdata\argenx\Efgartigimod\HAB40220\Biostatistics\Documentation\SAP

Author: Version Number: 3.0

Version Date: 02 May 2024

Template No.: CS\_TP\_BS016 Revision 7 Reference: CS\_WI\_BS005

Effective Date: 01Nov2021

Page 41 of 64

of PROMIS Fatigue as covariate. The visits included in the model will be baseline, weeks 2, 4, 12 and 24.

14.2.1.4. Change from baseline to week 24 in the PROMIS Cognitive Function Short Form 6a PROMIS Cognitive Function Short Form 6a assesses the frequency of cognitive difficulties experienced in the past 7 days. The questionnaire comprises 6 questions on subjective cognitive difficulties regarding a participant's concentration, memory, language, mental acuity, and perceived changes in cognitive functioning. The participant marks their response on a 5-point Likert scale, with lower scores indicating worse perceived cognitive functioning. Scores are converted to a T-score and received within the eCOA data transfers.

[figure not shown]
The number and percentage of participants with each individual PROMIS score will be summarized by treatment and time point, for the FAS for the IAWK12 and IAWK24. T-score will be descriptively summarized to present absolute value and changes from baseline for each visit.

For change from baseline to week 24 in PROMIS Cognitive, between treatment group difference will be analysed using longitudinal mixed model repeated measures (MMRM) as presented in section 14.1.1.1, except with change from baseline to week 24 in PROMIS Fatigue as the dependent variable and baseline value of PROMIS Cognitive as covariate using FAS for the IAWK12 and IAWK24. The visits included in the model will be baseline, weeks 4, 12 and 24.

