8.2.1.4. PROMIS

PROMIS is a publicly available system of highly reliable, precise patient-reported health status measures of physical, mental, and social well-being. PROMIS instruments measure concepts including pain, fatigue, and physical function.

 PROMIS Fatigue Short Form 8a: assesses the impact and perceived fatigue during the last 7 days. This validated 8-question scale has 5 response options, with scores ranging from 1 to 5. Scores are converted to a T-score, and higher scores indicate higher fatigue levels. A decrease in score (negative change from baseline) indicates improvement in fatigue.

[figure not shown]

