### 2. STUDY OBJECTIVES AND ENDPOINTS

### Table A: Objectives

Objectives	Endpoints
Primary	

 
Evaluate the efficacy of efgartigimod in reducing the severity of post-COVID-19 POTS symptoms.
 
Evaluate the safety and tolerability of efgartigimod in patients with post-COVID-19 POTS
 
	Change from baseline to week 24 in the Composite Autonomic Symptom Score 31 (COMPASS 31) (2-week recall version)  Change from baseline to week 24 in the Malmö POTS Symptom Score (MaPS)  Incidence and severity of adverse events (AEs), incidence of SAEs, changes in laboratory test results, vital signs, and electrocardiogram (ECG) results
Secondary	
Evaluate the efficacy of efgartigimod on patient global assessment of disease activity and fatigue	
 
Change from baseline to week 24 in the         Patient Global Impression of Severity (PGI-S)
 
Patient Global Impression of Change (PGI-C)         at week 24
 
Change from baseline to week 24 in the         Patient-Reported Outcomes Measurement
 

Document: BIOSdata\argenx\Efgartigimod\HAB40220\Biostatistics\Documentation\SAP

Author: [name] Version Number: 3.0

Version Date: 02 May 2024

Template No.: CS\_TP\_BS016 Revision 7 Reference: CS\_WI\_BS005

Page 13 of 64

	Information System (PROMIS) Fatigue Short Form 8a  Change from baseline to week 24 in the PROMIS Cognitive Function Short Form 6a
Assess the pharmacodynamic (PD) effect of efgartigimod	Absolute values, changes from baseline, and percent reduction from baseline in total IgG levels
Assess the pharmacokinetic (PK) profile of efgartigimod	Efgartigimod serum concentration-time profile
Assess the immunogenicity of efgartigimod	Incidence and prevalence of antidrug     antibodies (ADA) against efgartigimod
Exploratory	
_	

Document: BIOSdata\argenx\Efgartigimod\HAB40220\Biostatistics\Documentation\SAP

Author: Version Number: 3.0

Version Date: 02 May 2024

Template No.: CS\_TP\_BS016 Revision 7 Reference: CS\_WI\_BS005

Page 14 of 64

	9
--	---

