### 6.8. Common Calculations

For quantitative measurements, change from baseline will be calculated as:

Change from baseline at Visit X = Value at Visit X - baseline value.

A percent change from baseline can be calculated as.

• Percent change from baseline at Visit X = (actual value at Visit X -baseline value) \*100/baseline value.

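### The only between-group model for PROMIS Cognitive Function names change in PROMIS Fatigue as its response, and both PROMIS models list baseline as a visit

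*SAP*

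**What the plan says.** SAP Table A lists "Change from baseline to week 24 in the PROMIS Cognitive Function Short Form 6a" as a secondary endpoint, separate from PROMIS Fatigue 8a. SAP 14.2.1.4 carries that heading, and its model sentence begins "For change from baseline to week 24 in PROMIS Cognitive, between treatment group difference will be analysed". The sentence refers to the mixed model of 14.1.1.1 and then continues "except with change from baseline to week 24 in PROMIS Fatigue as the dependent variable and baseline value of PROMIS Cognitive as covariate".

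The visit list in 14.2.1.4 is "The visits included in the model will be baseline, weeks 4, 12 and 24". The list for the Fatigue model in 14.2.1.3 is "The visits included in the model will be baseline, weeks 2, 4, 12 and 24". Section 6.8 defines "Change from baseline at Visit X = Value at Visit X - baseline value". In 14.1.1.1, which both PROMIS models inherit, the COMPASS 31 and MaPS lists contain post-baseline weeks only, and the baseline score and its interaction with visit are already covariates.

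The two scales run in opposite directions. For Fatigue, protocol 8.2.1.4 states "A decrease in score (negative change from baseline) indicates improvement in fatigue". For Cognitive Function, SAP 14.2.1.4 describes the scale as one "with lower scores indicating worse perceived cognitive functioning".

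**The concern.** The model sentence in 14.2.1.4 contradicts itself: it announces an analysis of Cognitive Function and then specifies Fatigue as the outcome. No other current text corrects it, and everything else in that section is descriptive. A programmer must either follow the sentence and fit a second Fatigue model, or correct it silently and depart from the authorised SAP. If the output were labelled by its heading, a beneficial (negative) difference on Fatigue would read as a deterioration in cognition.

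The visit lists raise a separate, smaller question. A change score has no information at baseline, and the SAP does not say whether those rows enter the model. If they do, the covariance matrix has a zero row and the fit may pass down the fallback list in 14.1.1.1.

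**Working it through.** **1. Response variable: comparison of the text**

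| Place | Points to |
|---|---|
| SAP Table A; protocol section 3 | Cognitive, as its own endpoint |
| 14.2.1.4 heading | Cognitive |
| Opening of the model sentence | Cognitive |
| Covariate in the model sentence | Cognitive baseline |
| Post-baseline visits 4, 12, 24 | Cognitive (its window table in 6.3 has these weeks; Fatigue also has week 2) |
| Named dependent variable | Fatigue |

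Five indications point to Cognitive and one to Fatigue. The Fatigue model is already fully specified in 14.2.1.3. Run as written, 14.2.1.4 would give a second Fatigue model with the wrong baseline covariate and one visit fewer, and no model for Cognitive Function.

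**2. Baseline as a model visit, if zero rows are kept**

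Putting X = baseline into the 6.8 formula gives a change of 0 for every participant whose baseline record is the one in the baseline window.

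Inputs: N = 42 randomised 2:1, so 28 and 14 (protocol 1.1 and 6.3). With intercept, treatment and baseline slope at each visit, residual df = 42 − 3 = 39. Assumptions: complete data, equal visit variance v, and equal correlation r between post-baseline residuals, from 0.3 to 0.8. The documents give no PROMIS SD or correlation.

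*Rank.* The zero row leaves rank 3 of 4 (Cognitive) and 4 of 5 (Fatigue). Unstructured parameters rise from 6 to 10 and from 10 to 15. Without baseline the matrices are full rank, 3 of 3 and 4 of 4.

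*Structures with a separate baseline variance (UN, ANTE(1), TOEPH, ARH(1), CSH).* Each 100-fold cut in that variance lowers −2 REML log-likelihood by 39 × ln(100) = 39 × 4.605 = 179.6, without limit. There is no finite optimum. The FA0 and UNR steps only reparameterise UN and do not remove the problem.

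*Structures with one common variance.* Under CS the variance estimate is the mean of the diagonal:
- Cognitive: (0 + 3v)/4 = 0.75v, SE ratio √0.75 = 0.866
- Fatigue: (0 + 4v)/5 = 0.80v, SE ratio √0.80 = 0.894

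*CSH in closed form.* Given a zero baseline, the correlation between post-baseline visits is ρ/(1 + ρ), at most 0.5, and the variance is multiplied by (1 − ρ²). For r < 0.5, ρ = r/(1 − r), and the SE ratio is 1/√(1 − ρ²):
- r = 0.3: ρ = 0.4286, ratio 1.107
- r = 0.4: ρ = 0.6667, ratio 1.342
- r = 0.45: ρ = 0.8182, ratio 1.739
- r ≥ 0.5: diverges

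Week 24 SE with zero rows, relative to the fit without them (TOEPH and ARH(1) computed with baseline SD held at 0.001):

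| Structure | Cognitive | Fatigue |
|---|---|---|
| UN, ANTE(1) (covariances with baseline at zero) | 1.00 | 1.00 |
| TOEPH, r = 0.3; 0.4 | 1.107; 1.342 | 1.107; 1.342 |
| ARH(1), r = 0.3; 0.6 | 1.001; 1.055 | 1.001; 1.026 |
| TOEP, r = 0.3 to 0.8 | 0.862 to 0.838 | 0.889 to 0.847 |
| AR(1), r = 0.3 to 0.8 | 0.862 to 0.835 | 0.891 to 0.857 |
| CS, any r | 0.866 | 0.894 |

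Across the last three rows the SE is too small by 1 − 0.894 = 10.6% to 1 − 0.835 = 16.5%.

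*One nonzero baseline row.* In 500 simulated trials per endpoint at r = 0.3, 0.6 and 0.8 (assumed SD 8, one participant with a 3-point change inside the baseline window), the smallest eigenvalue of the residual covariance was 0.117. The unstructured fit is then finite and the week 24 SE ratio is 1.00.

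**The case against.** The best reply is that only one coherent reading of 14.2.1.4 exists, so a competent programmer would use Cognitive change and no wrong result would appear. Separate T-score summaries for each scale would also help expose a mix-up. The study is phase 2, tests no formal hypothesis and bases inference on precision. All this limits the damage. It does not change the fact that the sentence is the endpoint's only model specification and that the SAP requires analyses to follow the authorised text.

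On the visit lists, baseline may simply mean the visit that supplies the covariate, and the inherited 14.1.1.1 lists are post-baseline. That is a fair reading, and this part of the point is conditional for that reason.

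The standard-error ratios are illustrations. They rest on assumed correlations and complete data, and the TOEPH, ARH(1) and CSH figures describe fits with no finite optimum. They do not show the full range: ARH(1) for Fatigue at r = 0.8 is about 1.44. The draft code in 14.1.1.1 puts the baseline score in the CLASS statement; if that were carried over, 39 df would not apply. With complete data the df multiplies the whole REML criterion, so the ratios would not change. The single-nonzero-row case needs two records in the baseline window, and the protocol schedules only one PROMIS baseline assessment and none at screening.

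**Conclusion.** The concern holds. The response variable in 14.2.1.4 is wrong as written, which affects one of the four secondary efficacy endpoints and one of the two analysed by mixed model, at both the week 12 and week 24 analyses. This rests on the text alone.

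Listing baseline as a visit is a secondary fault in both PROMIS models. It does nothing if baseline change is left missing. If all-zero rows are kept, the week 24 standard error is essentially unchanged under a reported UN or ANTE(1) fit, can be too large under a degenerate TOEPH, ARH(1) or CSH fit, and is too small under TOEP, AR(1) or CS. Those sizes depend on the stated assumptions.

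The primary COMPASS 31 and MaPS models and the sample size are not touched. The text should be fixed, but the point does not threaten the trial's main conclusions.

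**What to change.** Make three edits to the SAP:

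1. In 14.2.1.4, set the dependent variable to change from baseline in the PROMIS Cognitive Function T-score.
2. In 14.2.1.3, delete baseline from the visit list, leaving weeks 2, 4, 12 and 24.
3. In 14.2.1.4, delete baseline from the visit list, leaving weeks 4, 12 and 24.

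Keep each scale's own baseline score as a covariate. The edits need no new data, do not alter the primary analyses, and have no downside.
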